Aim 3: To examine the effect of technology-enhanced TPC for FCGs on healthcare costs. Recognizing the synergy between FCGs and care recipients, we hypothesize that costs from all stakeholders (FCGs, care recipients, and health systems) of providing palliative care to care recipients in the intervention group will decrease compared to usual care. Using the Ambulatory and Home Care Record (AHCRR), which is rooted in the societal perspective,^{1,25} we will measure all costs of care for the FCG and care recipient, irrespective of payer.^{26,27} We hypothesize that there will be a net decrease in costs for 6 months post-enrollment from a societal perspective following

the addition of a TPC for FCG in the intervention group compared to the costs of care for the FCG and care recipient in the usual care group.

This revised application is responsive to **FOA PAR-16-250**: examining an innovative model of TPC for FCGs in underserved rural areas to address the public health imperative based on the rapid growth in the need for palliative care services.²⁸ Our study is designed to extend transitional and palliative care science to contribute to the 2016 strategic plan priority of the National Institute of Nursing Research of exploring novel approaches for effective interventions to provide compassionate support to FCGs of patients with life-limiting illnesses.

RESEARCH STRATEGY

A. SIGNIFICANCE

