Authentication of key biological and/or chemical resources. Findings regarding sex differences in FCG outcomes ^{9,152} have not been reported, although the majority of FCGs are female.¹⁵³ Based on the unequal sex distributions in other studies of FCGs,¹⁵⁴⁻¹⁵⁶ we anticipate the enrollment of FCG female participants will be greater than males. We have no evidence to suggest that the sex distribution of FCGs will impact our outcomes.

Variables and Their Measurements

Copies of instruments we will use are found in Appendix B, including core data elements for caregiving research suggested by the Palliative Care Research Cooperative Group.¹²⁹

Table 1 summarizes the concepts, variables and measures, and timing of data collection. Data, including sample characteristics (age, sex, race/ethnicity, marital status, education, how long the FCG has been providing care to the care recipient, any computer/Smartphone experience and availability) and questionnaires, will be collected by a study coordinator from all enrolled participants after obtaining consent (baseline) via in-person interviews prior to the care recipients' hospital discharge.

Self-reported data will be obtained by computer-assisted interviews, telephone or mailed questionnaires, based on FCGs preferences, from all FCGs at 2 weeks, at the end of the intervention period (Aims 1 and 2) and at 6 months (Aim 2). If FCGs choose to complete questionnaires independently, they will have the choice of receiving a packet by mail or a link to complete questionnaire electronically via REDCap. If any FCG would like assistance completing the questionnaires, the study coordinator will provide assistance. Given the complexity of cost data, participants will be telephoned monthly for 6 months post-hospital discharge for cost data collection needed to address Aim 3.

If the care recipient dies, we will collect Aims 1 and 2 outcomes data from the FCG approximately 2 weeks later, given that grieving family members' distress and satisfaction with care should be more stable 2 weeks after their loved one's death.^{157,158}

In order to assure the safety of participants, the intervention nurse or study social worker will follow up by phone with all participants, regardless of, who report a score of >10 on depressive symptoms on any questionnaire or if an intervention or control caregiver reports via phone, survey or email information that raises the concern for elder mistreatment or abuse about family or

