Aim 3: Examine the effect of technology-enhanced TPC for FCGs on healthcare costs. The Ambulatory and Home Care Record (AHCR) will be used as our healthcare cost measure. The AHCR is designed to capture costs from a societal perspective, implying that costs from all stakeholders (FCG, care recipients, and health systems) will be collected. Developed for the Canadian health system where healthcare is primarily publicly funded,¹ the AHCR will be modified for our study to collect expenditures paid for by any type of payer (e.g., commercial, government, or other insurance; and self-pay/no insurance) instead of simply publicly-financed expenditures as in the original AHCR. Third party insurance refers to any supplemental insurance over and above the primary insurance that the patient has (see Table 2). Thus, the proposed change to the original AHCR measure is only to increase clarity regarding funders and therefore we do not anticipate any threat to the AHCR's validity. The AHCR captures self-reported utilization and cost information for care provided by all FCGs and other unpaid caregivers, paid care received at home (e.g., home health care) and outside of the home (e.g., doctor/therapy appointments), as well as medications, supplies, and equipment. Out-of-pocket costs refer to all care-related expenses not paid for by the insurance. These data will be collected monthly for 6 months following each care recipient's discharge from the index hospitalization to minimize recall bias and to account for any time lag in billing systems. The FCGs will be prompted to have all bills received during the preceding month available during the monthly AHCR data collection. Agreement between care recipients' reports on the AHCR and administrative data range from moderate ($\kappa=0.41$; 95 percent confidence interval, 0.16–0.61) for physician visits to perfect ($\kappa=1.0$) for physical therapy visits.²⁵

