For analyses of costs, standard descriptive statistics including mean, median, standard deviation, minimum and maximum will be provided for all cost outcomes measured individually and also for the overall cost measure. The difference in overall cost between the intervention and control group will provide an estimate of the cost impact of the TPC for FCG model of care. The difference in hospitalization and ED costs between the treatment and control arms will determine the cost avoidance potential of implementing the intervention. The difference in FCG cost, a component of the overall costs, between intervention and control groups will provide evidence on the impact of the intervention on this specific cost component. Both the descriptive and multivariable-adjusted measures will be estimated for 8 weeks and 6 months. Because the distribution of healthcare costs and length of stay (LOS) are generally skewed, both the LOS and costs will be log-transformed before any estimation; the estimated coefficients can then be interpreted as the approximate percentage changes. Alternatively, we will also explore modeling costs and LOS with a generalized linear model with gamma distribution and log link.¹⁸³ Furthermore, to account for the possibility that some of the study patients will die before the six-month follow-up; we will also apply econometric methods of censored regression.^{184,185}

Data Management

Following the data safety monitoring plan (see Protection of Human Subjects), the PI and investigative team will review the data to ensure quality, adherence to study procedures, and safety at monthly study team meetings. All participant data will be coded and stored in a secure, locked cabinet in the study coordinator's office. All data will be entered into the web-based Research Electronic Data Capture (RED-Cap) database and maintained on secure, password-protected servers, accessible only to members of the study team. The database will be exported to the statistical analysis package, SAS, to be analyzed anonymously, and standard Mayo Clinic policies and safeguards will be used to protect the confidentiality of the subject records.

Expected Outcomes

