schedule data collection will be made approximately 2 weeks and then monthly after hospital discharge at the number and time of day the FCGs suggest. Depending on the participant's preference, they may choose to be contacted by text message or email instead of receiving a phone call. The study coordinator will use a cell phone with caller identification recognizable to the participants to assure completeness of follow-up data. If at first we are unable to connect, phone calls will be made at varying times during the day. Our prior experience related to completion of data collection after hospital discharge indicated that the majority of patients and FCGs do not venture far from home soon after discharge. We will provide remuneration to all FCG participants commensurate with the time spent in the study (intervention activities for intervention group, data collection for both groups) to encourage continued engagement. If a care recipient dies during the data collection period, it may be difficult to collect subsequent data from the FCG. Providing reminder phone calls as an attention control device will augment the continued engagement of control FCGs in the study. Recall of cost components will be enhanced by monthly data collection up to six months after the care recipient's index hospitalization to account for any time lag in billing systems. The FCGs will be provided a checklist and prompted to have all bills received during the preceding month available during the monthly AHCR data collection.

Resource Sharing Plan/Data Sharing Plan

The research will be disseminated at national scientific meetings, and manuscripts will be generated from the Specific Aims. A clean de-identified dataset will be available to qualified investigators through communication with the PI after primary results manuscripts are accepted.

C. Timetable

STUDY TIME LINE	Year 1				Year 2				Year 3				Year 4				Year 5			
	Tasks	Q1	Q2	Q3	Q4	Q1	Q2	Q3												
Study start-up: regulatory & training																				
Subject accrual & data collection																				
Data Analysis																				
Cost Analysis																				
Dissemination & final report																				

D. Future Directions

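### Cost collection is keyed to when bills arrive and ends with the 6-month cost window, so the stated allowance for billing lag fails for billed services late in that window

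*Combined protocol and SAP*

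**What the plan says.** The combined protocol and SAP sets the collection schedule under Variables and Their Measurements: "participants will be telephoned monthly for 6 months post-hospital discharge for cost data collection needed to address Aim 3". The Aim 3 text of that section ties the Ambulatory and Home Care Record (AHCR) to the same period, which starts at "discharge from the index hospitalization to minimize recall bias and to account for any time lag in billing systems". The instruction to caregivers is: "The FCGs will be prompted to have all bills received during the preceding month available during the monthly AHCR data collection".

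The billing-lag rationale is repeated under Data collection after hospital discharge, where recall is to be helped by "monthly data collection up to six months after the care recipient's index hospitalization to account for any time lag in billing systems".

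The Analytical Plan for Aim 3 names two windows: "Both the descriptive and multivariable-adjusted measures will be estimated for 8 weeks and 6 months". The Aim 3 hypothesis in the Specific Aims starts the clock elsewhere: "there will be a net decrease in costs for 6 months post-enrollment from a societal perspective". Enrollment takes place during the index hospital stay, so it precedes discharge.

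The AHCR does not rest on bills alone. It takes self-reported use and cost, a worksheet modelled on Table 2 helps caregivers keep track, and caregiver time is valued from Bureau of Labor Statistics earnings. The text supplied contains no rule that assigns a bill to its date of service, none that includes or excludes the index stay, no collection after month 6, and no price for a service that has been used but not yet billed. Censored regression is planned for deaths before six months, not for billing lag.

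**The concern.** A monthly call that asks for bills by month of receipt records cost when the paperwork arrives, not when care was given. For a service early in the window this does little harm, because a later call picks up the bill. For a service near the end there is no later call. The caregiver can report that the admission or emergency department (ED) visit took place, but may not yet know the insurer payment or the out-of-pocket share.

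The items most exposed are hospital, ED, ambulatory and third-party amounts. Readmission and ED costs are the ones the plan uses to estimate costs avoided. The same receipt-based prompt raises two allocation problems: bills for care in the first 8 weeks may arrive after week 8, and bills for the index stay may be brought to the calls in months 1 and 2 and counted as early follow-up cost.

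**Working it through.** The plan gives no figure for billing lag, so there is nothing to reproduce. The check compares the end of collection with the end of the window, and then shows how the size depends on an assumed lag.

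1. **Time left for late bills.** Collection ends at discharge + 6 months.
   - Window from discharge: it ends at discharge + 6 months, so the time left is 0.
   - Window from enrollment: it ends at enrollment + 6 months, so the time left is the enrollment-to-discharge stay.

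2. **Share of billed 6-month cost arriving after the last call** (window from discharge). Assume constant use and a fixed lag of L months; the share is L/6.
   - L = 0.5: 0.5/6 = 8.3%
   - L = 1: 1/6 = 16.7%
   - L = 2: 2/6 = 33.3%

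   If the lag is exponential with mean L, the share is (L/6)(1 − exp(−6/L)), which gives 8.3%, 16.6% and 31.7%. The shape of the lag matters little.

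3. **Window from enrollment.** With an assumed stay of d days after enrollment, the share is (L − d/30.4375)/6. For d = 3 to 14 days it is 15.0% to 9.0% at L = 1, and 31.7% to 25.7% at L = 2. The problem shrinks but remains.

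4. **Effect on the contrast.** Sample Size and Power Calculations assumes $2,000 per month. Treat that as billed cost and assume, for illustration, a 20% saving ($1,600 per month).
   - Full 6 months: $12,000 against $9,600; difference $2,400, ratio 0.80.
   - 1-month lag (5 months billed): $10,000 against $8,000; difference $2,000, ratio 0.80.
   - 2-month lag (4 months billed): $8,000 against $6,400; difference $1,600, ratio 0.80.

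   The absolute difference shrinks with the missing share. The ratio, which is what log-transformed costs or a log-link model estimates, does not move.

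5. **8-week window.** With a 30-day lag, 30/56 = 54% of billed 8-week cost arrives after week 8; with 60 days, all of it does (60/56 > 1). But calls continue for about 182 − 56 = 126 days after week 8, longer than either lag. These bills can be collected. What is missing is a stated rule that puts them in the 8-week window.

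6. **Index-stay bills.** Two months at $2,000 is $4,000, against $3,200 with the assumed 20% saving. Add an assumed index bill of $4,000 to each arm: $8,000 against $7,200, a saving of 800/8,000 = 10%. Over six months: $16,000 against $13,600, or 2,400/16,000 = 15%. The absolute difference is unchanged; the percentage effect is diluted, and variation in index bills adds noise.

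**The case against.** The strongest reply is that the plan has more than bills to work with. Self-report, the worksheet, valued time, travel and point-of-sale spending need no later bill, and counts of hospitalizations and ED visits need none either. This stands, and it confines the point to bill-dependent items. It does not remove the point: reporting a visit does not supply an amount the caregiver has not been told, and no other price source is stated.

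The second reply is that monthly repetition does pick up lagged bills. It does for most of the window, so the plan's billing-lag statement is too broad but not wrong throughout.

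Four stronger readings are tempting and are not supported:

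- A reader might infer that the 8-week estimate loses 54% to 100% of its billed cost. Nothing in the plan closes the data at week 8, so this is a risk of misallocation, not a loss.
- A reader might infer that every Aim 3 estimate is pulled towards no effect. On the percentage scale of the Analytical Plan, an equal proportional loss has no such effect. Equal loss is itself an assumption; if the timing of services differed between arms it need not hold, and the documents do not settle the direction.
- A reader might infer that index-stay bills create a spurious group difference, or lie wholly outside the intervention's reach. Bills for care before randomization should balance on average. The intervention also begins before discharge, and part of the stay lies inside a window that starts at enrollment.
- A reader might infer that the AHCR form records no service dates. The instruments are in Appendix B, which is not in the text supplied, so this is unknown. Even if dates are recorded, the analysis plan gives no rule for using them.

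**Conclusion.** The concern holds for bill-dependent costs. The schedule covers billing lag early in the 6-month window but not at its end, where the time left for bills is zero or only the remaining index stay. On an assumed fixed lag of 0.5 to 2 months, constant use and a window from discharge, about 8% to 33% of billed 6-month cost would be missed. The true size is unknown, because the plan gives no lag and deaths before month 6 will break constant accrual for some care recipients.

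The consequence is understated total cost and a smaller absolute difference, including the avoided-cost estimate. The 8-week costs, and the treatment of index-stay bills, depend on an attribution rule that is not stated. Time, travel, point-of-sale costs and utilization counts are largely unaffected. The change should be made: it is cheap, and without it the billed part of both the 8-week and the 6-month costs can be misstated.

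**What to change.** 1. Use one start for the cost window, reconciling the post-enrollment wording of the Aim 3 hypothesis with the post-discharge wording of the AHCR section.
2. Record the service date for each bill, if the AHCR form does not already do so. Assign cost to the 8-week and 6-month windows by that date, and use later calls to complete the 8-week window.
3. Exclude charges for services dated before the window opens, including the index stay to that extent.
4. At the month-6 call, list services used but not yet billed. Value each as reported use times the mean cost of billed services in the same category, with a sensitivity analysis.
5. Limit the billing-lag statement to services before the final weeks of the window.

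The cost is at most one date field on the form, one list at the last call and a short analysis rule; no extra call is needed. The downside is that some late-window costs are imputed from unit costs and not taken from actual bills. Hospital costs are skewed, so a category mean is a rough price; this is why the sensitivity analysis is needed.

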We will report these measures, per subject, every month to minimize the impact of patients dying in the earlier part of the intervention interval. The difference in costs of readmissions and ED visits between the intervention and control patients will provide an estimate of the costs avoided due to the proposed intervention. We anticipate that some care recipients will die before 6 months and therefore we will need to address right censoring of utilization and costs due to patients dying before the end of the study. Accordingly, we will adopt appropriate econometric methods as described in the **Analytical Plan section below** to account for the possible censoring of utilizations and costs.

The time costs refer to the FCGs' time and, if the FCG is employed, the employer time lost in the course of

Table 2: Modified Framework for Assessment of Palliative Care Costs¹		
Expenditure Category	Privately-incurred Costs	Time Costs
Third party-incurred Costs (Commercial/ Medicare/ Medicaid/ Other/ No Insurance)		
3rd Party Insurance Reimbursement (Yes/No)	Out-of-Pocket	Caregiver lost time from
• Home-based services	• Home-based services	• Labor Market
• Ambulatory appointments	• Ambulatory appointments	• Household work
• Hospitalization	• Hospitalization	• Leisure
• Emergency Department Visits	• Emergency Department Visits	
• Facility care	• Facility care	
• Medications	• Medications	Employer Time Loss
• Supplies and Equipment	• Supplies and Equipment	
	• Paid house work	
	• Travel expenses	
Total 3rd party Expenditures	Total Out-of-Pocket Expenditures	Total Time Cost

providing care to the care recipient. Time costs for the FCGs will be valued by a human capital approach.¹⁸⁰ The most recently available data on current earnings by age and sex from the Bureau of Labor Statistics (BLS) will be used to impute the market value of time withdrawn from leisure and household work. In order to value lost time from the labor market, age- and sex-based earnings from the BLS will be adjusted for employer-paid benefits, vacations days and holidays.

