Aims 1 and 2. Statistical analyses of Aims 1 and 2 will be performed in a similar manner. Every FCG will be evaluated using various scales and survey instruments at baseline, 2 weeks, and 8 weeks post patient discharge (Table 1). We will use a response-feature analysis as our primary approach in analyzing these repeated measures data.¹⁸¹ For each FCG, the magnitude of the scores from the respective instruments will be plotted versus time (measured in months); least squares regression will be used to estimate a participant-specific rate of increase in points per month. This slope parameter estimate will be used as the response feature for each participant and is the primary endpoint for this study. The primary analysis of this endpoint will be analyzed using a two-sample t-test or Wilcoxon rank-sum test, as appropriate. The endpoints will also be analyzed using a fixed-effects linear regression model. This model will use the estimated regression-slope response-feature as the dependent variable and have independent variables consisting of intervention (yes, no) as well as any baseline covariates such as FCGs’ age, employment status, etc. These analyses will adjust for any possible imbalances in these baseline covariates among FCGs that occur due to the randomized assignment to the intervention. This analysis approach will hold for those endpoints collected only at two time points (i.e., baseline and 8 weeks).

Aim 3. Descriptive statistics, including mean, median, and standard deviation (minimum and maximum) for the utilization measures (i.e., hospitalizations and ED visits) will be provided. Considering the count nature of the utilizations, and to also account for any potential differences between the baseline characteristics of the care recipients in the two study arms, we will use Poisson regression to model various utilization outcomes.¹⁸² We expect that the gains (decreased healthcare utilization and costs) will be sustained beyond the enrollment period. Therefore, both descriptive and multivariable-adjusted measures will be estimated for the intervention period and the subsequent months post-intervention. A limitation of this economic approach will be the memory recall of the FCGs. We will provide a worksheet similar to Table 2 for all participants to help them track services and costs.

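### Death of the care recipient is coded as right censoring of cost, so the added censored-regression analysis targets cost had nobody died, not the 6-month cost that Aim 3 hypothesises

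*Combined protocol and SAP*

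**What the plan says.** The Specific Aims (Aim 3) hypothesise that "there will be a net decrease in costs for 6 months post-enrollment from a societal perspective", and say of scope that "we will measure all costs of care for the FCG and care recipient, irrespective of payer".

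Variables and Their Measurements (Aim 3) names death as the censoring event: "we will need to address right censoring of utilization and costs due to patients dying before the end of the study". It refers the reader to the Analytical Plan for the method. It also offers a second device: "We will report these measures, per subject, every month to minimize the impact of patients dying". It does not say whether care recipients who have died stay in the monthly denominator at zero.

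The Analytical Plan (Aim 3) gives descriptive statistics, the between-arm difference in overall cost, a regression in which "both the LOS and costs will be log-transformed before any estimation", and an exploratory gamma model with log link. Then, because "some of the study patients will die before the six-month follow-up", it says that "we will also apply econometric methods of censored regression". Death is the only reason given for that last analysis. For utilization, "we will use Poisson regression to model various utilization outcomes", with no exposure time and no rule for deaths.

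**The concern.** Censoring means that the quantity of interest exists but was not fully seen. For the care recipient's own care over a fixed six months, death in month 2 hides nothing of that kind: use and cost accrue to death and are zero for the rest of the window. A right-censored regression treats the accrued total as a lower bound on a larger unseen total, and so credits the person with care never delivered. Its target is spending in a world without deaths, which is not the Aim 3 hypothesis.

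The event that does fit the definition is a caregiver who stops answering the monthly calls while the care recipient is alive. The sample-size section allows for about 30% attrition, yet no cost method is assigned to that case.

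At stake is the direction as well as the level of the Aim 3 result. If more care recipients survive in one arm, that arm truly incurs more months of cost, and a censoring analysis removes that difference. The Significance section cites a study in which early palliative care went with better survival, so a difference cannot be ruled out, although the intervention here is directed at caregivers and the plan predicts no survival effect.

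**Working it through.** The plan states no mortality, no survival difference and no expected six-month cost, so there is no figure of its own to reproduce on this point.

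**Inputs**
- Monthly cost $2,000 in both arms, SD $1,000 (Sample Size and Power Calculations).
- Window of 6 months (Specific Aims, Aim 3).
- Six-month mortality p: assumed, shown as a range.
- Constant death rate and no extra cost near death: assumed, the latter relaxed below.

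**Level**
- Death rate per month: L = -ln(1 - p)/6.
- Mean months alive in the window: m = (1 - exp(-6L))/L = p/L.
- Actual mean cost: $2,000 × m. No-death cost: $2,000 × 6 = $12,000.
- Overstatement: 6/m - 1.

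| Assumed p | m (months) | Actual mean cost | No-death cost | Overstatement |
|---|---|---|---|---|
| 20% | 5.378 | $10,755 | $12,000 | 12% |
| 40% | 4.698 | $9,397 | $12,000 | 28% |
| 60% | 3.929 | $7,858 | $12,000 | 53% |

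This is the gap between the two targets. It is not the output of a fitted model.

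**Between-arm difference, closed form.** Suppose that the intervention is 5% cheaper per month ($1,900). The no-death difference is then 6 × ($1,900 - $2,000) = -$600 whatever the mortality. The actual difference depends on survival:
- Mortality 50% in both arms (m = 4.328): 4.328 × (-$100) = -$433. Same sign.
- Control 50%, intervention 45% (m = 4.516): $1,900 × 4.516 - $2,000 × 4.328 = about -$75. Same sign, saving exaggerated.
- Control 50%, intervention 40% (m = 4.698): $1,900 × 4.698 - $2,000 × 4.328 = about +$271. Opposite sign.

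**Fitted models.** These simulations used 100,000 per arm, with deaths entered as right-censored. The first three rows use log cost, a stable gamma-distributed monthly cost for each person, and an intervention 5% cheaper per month. Entries are intervention/control cost ratios.

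| Mortality, control vs intervention | Cost at death | Actual ratio | Censored lognormal | Log regression on accrued cost |
|---|---|---|---|---|
| 50% vs 50% | none | 0.95 | 0.96 | 0.95 |
| 50% vs 40% | none | 1.03 | 0.92 | 1.08 |
| 50% vs 40% | $5,000 (assumed) | 0.98 | 0.89 | 0.98 |

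In the rows without a cost at death, the fitted control mean is about $13,800 against an actual mean of about $8,650. It exceeds even the $12,000 no-death figure, because cost accrued at death depends on the person's own cost rate, so the censoring is informative on the cost scale.

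**Sensitivity to within-person correlation.** Take equal monthly cost, with 40% control and 50% intervention mortality. The actual difference is $8,656 - $9,397 = -$741. A normal censored model on dollars gave +$330 to +$386 across runs when each person keeps one monthly cost, and +$69 to +$87 when each month is drawn independently. The sign is wrong both ways, but the size varies several-fold.

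**The case against.** Four objections have weight.

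- **The outcome is societal.** A reader might infer that all cost after death is nil and that nothing is hidden. The documents do not support that. The total includes caregiver time and out-of-pocket cost (Table 2). Bereavement support for intervention caregivers runs to the end of week 8 (At home technology-enhanced intervention). Bills may lag. The section on potential problems warns that data may be hard to obtain from the caregiver after a death. Zero after death holds only for the care recipient's own care; other items may be truly missing.
- **Censored regression is an additional analysis.** A reader might infer that every planned six-month cost result is overstated. That does not follow. The descriptive difference and the log-cost and gamma models on accrued costs do not inherit this error, and log regression on accrued cost kept the true sign in the table above. What remains is that no rule says how deaths enter those models, no cost analysis is named primary, and censored regression is offered as the remedy for deaths, so its result could be read as the corrected one.
- **The estimator cannot be identified.** The two sources cited for it, 184 and 185, lie beyond the printed reference list, which ends at 166. Some censored-cost estimators treat death as terminal. The plan's own words make death the censoring event, so clarification is needed on either reading.
- **Reversal is not a prediction.** It needs a material survival gap, a high cost near death can remove it, and the mortality values are assumed. With 100 per group, the standard error of the raw mean difference in the equal-cost example is about $640 to $890, so a single trial might not show the reversal clearly. Aim 3 is also not the aim on which the sample size rests.

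**Conclusion.** The concern holds for the added censored-regression analysis. As written, the plan treats death as right censoring, and following that rule estimates six-month cost had nobody died. With $2,000 per month, a constant death rate and no extra end-of-life cost, that target exceeds actual mean cost by 12% to 53% for assumed mortality of 20% to 60%. If survival differs between arms, the estimated difference is biased and can have the wrong sign. This is a possibility whose size depends on the mortality gap, within-person cost correlation and cost near death, none of which the documents give. With equal mortality, the simulated cost ratio was close to the truth and only the level was wrong.

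This is a wrong rule rather than a missing detail, but it sits in a supplementary model for a non-primary aim. Severity: should fix.

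**What to change.** In the Aim 3 measures and the Aim 3 analysis of costs:

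- Define death of the care recipient as a terminal event. Set care-recipient utilization and cost to zero from death to month 6, and compare mean six-month totals over all randomized pairs.
- Keep caregiver costs as reported to month 6, including after a death.
- Reserve censoring or missing-data methods, such as inverse-probability-weighted monthly costs, for loss to follow-up while the care recipient is alive and for caregiver reports or late bills missing after a death.
- Report survival by arm beside cost.
- State the exposure time in the Poisson model, and whether care recipients who have died stay in the monthly denominators.
- Supply the missing references, or name the estimator.

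The cost is wording and some extra programming. Date of death is not listed as a data item, so confirm that it is recorded. The change does not recover caregiver costs that go unreported after a death; those remain a missing-data problem.
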